
## **6. SPECIFIC AIMS**

1) To implement the CHARM 2 GE+FP intervention, comprised of CHARM sessions with men and parallel sessions with women, and inclusive of broader contraceptive options including LARC, as well as one combined couples session. Men's sessions will be delivered by male health providers; women's sessions will be delivered by public Auxiliary Nurse and Midwives (ANMs), or a trained provider/counselor. The couple's session will be delivered by an ANM, trained provider, or counselor.

2) To evaluate the impact of CHARM2 on spacing contraceptive use (including LARC), unintended pregnancy, and MSV via a two armed cluster RCT with N=1200 married couples from 20 geographic clusters (n=60 couples per cluster) in rural India. The control arm will receive SOC in the form of community health workers offering pills/condoms and linking women to public health clinics. Outcomes will be assessed via pregnancy testing and surveys at baseline, 9 and 18-month follow-ups.

**Hypotheses:** We hypothesize that CHARM2 participants will be more likely than SOC participants to:

- a) Use contraception (including LARC) at 9 & 18-month follow-ups; effects on LARC will be explored
- b) Be less likely to report marital sexual violence (MSV) at 9 & 18-month follow-ups
- c) Not have an unintended pregnancy over the 18-month follow-up period.

3) To assess the quality, scalability, and replicability of CHARM2 for uptake by rural health systems (i.e., sustainability), using implementation science methods including IDI with CHARM2 couples (n=50) and providers (n=20), 5-7 focus groups with MILs of couples that participate in IDIs, control condition couples (n=20), and key stakeholders from the FP and rural health infrastructures at state, national and international levels (n=50), survey of healthcare facilities in the study area (n approximately=250), and a cost-effectiveness analysis.

Should CHARM2 prove effective and sustainable, study findings will have broad implications for FP interventions for low resource settings in India and elsewhere.

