**Procedures/Activities for Participants:** Phase 1 of the study is preparatory stage for cluster randomization and training of providers. In phase 2 and phase 3, the participants will participate in the trial at the villages where they reside. NIRRH staff will conduct survey assessments with participants in the homes of the participants, after obtaining permission to do so. Intervention sessions with male providers and ANMs or trained providers/counselors will take place in at home, or in clinic settings. In Phase 2, the participants will complete survey assessments at baseline, and 9 &18-month follow-up. Female participants (wives) will also take urine pregnancy tests at baseline, and 9 &18-month follow-up. In phase 3 a subsample of CHARM2 couples (n=50) will participate in IDIs at 9 month follow-up to describe their experiences with the intervention and their views of its utility, as well as their perceptions related to its outcome effects. All CHARM2 providers (n=20) will be asked to participate in IDIs at their facility to assess their perceptions of CHARM2 quality, acceptability and utility. A subsample of control condition couples (n=20) will participate in IDIs at 18 month follow-up to describe their experiences with family planning and gender-based violence in the study area context but outside of the intervention. Healthcare facilities in the area will be mapped and information will be collected on whether the facility provides family planning, what methods they provide, and whether the facility participated in the CHARM2 intervention.

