**Data Analysis:** The primary comparison of the binary outcomes between intervention groups at 9 & 18-months will use mixed-effects longitudinal logistic regression, with random effects for the individual (couple) and for geographical clusters, over time. Baseline will be included as a time point (Aims 2a, 2b only). A categorical time effect will be used (profile model). A “difference-in-differences” analysis will compare the treatment arms. Statistically, this amounts to testing for an interaction between time and treatment arm in the longitudinal model. In addition, the intervention groups will be compared via a generalized estimating equations (GEE) logistic regression analysis. The GEE models will use a nested exchangeable working correlation matrix that takes into account geographic clusters and the individual (couple) within the cluster. No other covariates will be included in the primary analysis. Since the treatment assignment is at random this “un- adjusted” analysis will provide a causal effect of the intervention. However, we will also conduct secondary analyses, adjusting for potentially relevant covariates (e.g., age, current pregnancy, past year child- birth, etc.), in addition to time and treatment arm, using backward model selection at the  $\alpha=0.15$  threshold level. These secondary analyses may improve precision (power) of estimating the treatment effect and reduce any bias due to random imbalances between arms.

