- a) Based on CHARM, we expect the proportion of women using modern contraception in the control group to be 40% at 18 month follow-up. This study will have 83.3% power to detect an absolute difference of 12% or more between treatment groups at follow-up, or 40% vs 52% in the two groups, with total kappa [variance]=0.10, assumed to be split equally between within-village variance and within-cluster variance . These values were found in the CHARM study.
- b) Based on CHARM, we expect that 89.2% of women in the control group will report no recent MSV at 18 month follow-up. We have 91.5% power to detect an absolute difference of 6% or more between treatment groups (89.2% vs. 95.2%) with kappa=0.036,

assumed to be split equally between within-village variance and within-cluster variance. The effect size of 6% difference and the kappa=0.036 were observed in the CHARM study.

c) Based on CHARM, we expect the proportion of women with no unintended pregnancy over 18 month follow-up to be 90% in the control group. This study will have 89.5% power to detect an absolute difference of 5.5% or more between groups (90% vs. 95.5%), with kappa=0. The effect size of 5.5% difference is based on a meta-analysis of cluster RCTs evaluating impact of FP interventions on unintended pregnancy (with comparable measures to this study). The study showed a 50% reduced risk for intervention participants with no unintended pregnancy in the CHARM group, or 5.5%. The kappa=0 is based on the CHARM study, where no significant intra-cluster correlation was found for this outcome.

While we will use longitudinal mixed effects logistic regression methods in our analyses, for power calculations we considered only the 18-month time point in a model similar to those to be used in the analyses. Power for the prescribed longitudinal analyses will be higher. Power calculations for each hypothesis used statistical simulations with 10,000 iterations. The conversion from kappa to the random cluster effect was done using the delta method, and was confirmed through the simulation.

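### The only test named for the binary outcomes is a time-by-arm interaction, which for unintended pregnancy (Aim 2c, no baseline record) either measures change in effect between visits or does not exist

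*Combined protocol and SAP*

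**What the plan says.** Section 9, Data Analysis, gives one procedure for all three hypotheses: "The primary comparison of the binary outcomes between intervention groups at 9 & 18-months will use mixed-effects longitudinal logistic regression", with random effects for couple and cluster. Time is coded by visit: "A categorical time effect will be used (profile model". The arms are compared by difference-in-differences, which the section defines: "Statistically, this amounts to testing for an interaction between time and treatment arm in the longitudinal model". The same paragraph restricts the baseline record: "Baseline will be included as a time point (Aims 2a, 2b only". It then adds a second model, "In addition, the intervention groups will be compared via a generalized estimating equations (GEE) logistic regression analysis", without saying which term is tested.

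Aim 2c is hypothesis (c) in Section 6: "Not have an unintended pregnancy over the 18-month follow-up period". Pregnancy is tested three times: "Female participants (wives) will also take urine pregnancy tests at baseline, and 9 &18-month follow-up". Sample size considerations, item c, powers this outcome at 89.5% for 90% against 95.5% of women free of unintended pregnancy, with kappa 0. On how power was computed, the section says "for power calculations we considered only the 18-month time point in a model similar to those to be used in the analyses".

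**The concern.** Difference-in-differences needs a reference measured before treatment. Aims 2a and 2b keep baseline, so for them the interaction compares change from baseline between the arms, as intended. Aim 2c has no baseline record in the model, and the paragraph gives it no different test. Two readings remain.

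- **Two records per woman (months 9 and 18).** The interaction is the month-18 log odds ratio minus the month-9 log odds ratio. An intervention that lowers pregnancy equally in both halves of follow-up gives a value near zero.
- **One record per woman (any unintended pregnancy over 18 months).** There is no time factor, so the named test is undefined.

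Under neither reading does the named test address hypothesis (c). This outcome is in the trial's title. Section 15 plans an interim efficacy look with an O'Brien-Fleming rule, and the cost-effectiveness analysis takes unintended births averted from the outcome analyses. Both need a defined effect estimate. If the test is settled only once data are in hand, the choice among several possible contrasts is open to the results.

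**Working it through.** **Inputs.** From Sample size considerations: 18-month risk of unintended pregnancy 10% (control) and 4.5% (CHARM2), kappa 0, and 960 observed couples. Section 9 interviews 50 couples at 5 per intervention cluster and 20 at 2 per control cluster, so there are 10 clusters per arm and 10 × 48 = 480 couples per arm. Assumed, because the documents do not give them: two-sided alpha 0.05 and the split of risk between the two 9-month intervals.

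**Step 1. Reproduce the stated 89.5%.** Wald test of the 18-month log odds ratio:

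- Log OR = ln(0.045/0.955) − ln(0.10/0.90) = −0.858.
- SE = √[1/(480 × 0.10 × 0.90) + 1/(480 × 0.045 × 0.955)] = √(0.02315 + 0.04848) = 0.268.
- Power = Φ(0.858/0.268 − 1.96) = Φ(1.245) = 89.3%.

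Other versions of the two-proportion test give 90.9% (pooled), 91.1% (unpooled) and 88.7% (continuity-corrected). The stated figure is therefore the power of a direct arm comparison at month 18.

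**Step 2. The interaction under constant hazard, cumulative status at each visit.**

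- Month-9 risk = 1 − √(1 − 18-month risk): 5.13% control, 2.28% CHARM2.
- Odds ratios: 0.431 at month 9 and 0.424 at month 18. Log ORs: −0.843 and −0.858. Interaction = −0.015.
- Variance of the month-9 log OR = 0.1365; of the month-18 log OR = 0.0716.
- Covariance: a woman counted at month 9 is also counted at month 18, so each arm contributes 1/[n(1 − p9)p18]. That is 1/(480 × 0.9487 × 0.10) + 1/(480 × 0.9772 × 0.045) = 0.0220 + 0.0474 = 0.0693.
- SE of the interaction = √(0.1365 + 0.0716 − 2 × 0.0693) = 0.264.
- z = −0.015/0.264 = −0.06, so the rejection rate is 5.0%, which is alpha.

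Simulation agrees. In 20,000 trials under constant hazard, the interaction rejects in 5.1% (cumulative status) or 4.6% (new events per interval), and the 18-month arm comparison in 91.4%.

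**Step 3. Let the effect change over time.** The 18-month risks stay at 10% and 4.5%; only the timing moves. Each row is 10,000 simulated trials with two records per woman, a saturated visit-by-arm logistic model and Wald tests allowing for within-woman correlation.

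| Outcome record | Timing | Control, months 9 / 18 | CHARM2, months 9 / 18 | Interaction (log OR) | Interaction rejects |
|---|---|---|---|---|---|
| Cumulative | even | 5% / 10% | 2.25% / 4.5% | −0.03 | 4.4% |
| Cumulative | late | 5% / 10% | 3.5% / 4.5% | −0.49 | 69% |
| Cumulative | early | 5% / 10% | 1.0% / 4.5% | +0.79 | 35% |
| Per interval | even | 5% / 5% | 2.25% / 2.25% | 0 | 4.3% |
| Per interval | late | 5% / 5% | 3.5% / 1.0% | −1.28 | 55% |
| Per interval | early | 5% / 5% | 1.0% / 3.5% | +1.28 | 55% |

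The total benefit is identical in every row. The interaction rejects anywhere from about 4% to 69% of the time, and in the early-effect rows its sign points against the intervention.

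**Step 4. Direct contrasts on the same even-timing data.** The month-18 arm contrast has 91.2% power with cumulative status and 61.9% with interval events. The arm effect averaged over visits has 83.9% (cumulative) or 90.9% (interval). Leaving the contrast unnamed therefore spans roughly 62% to 91%.

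Sample size considerations adds that the longitudinal analyses will have more power than the month-18 calculation. For the interaction with a constant effect, the reverse holds.

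**The case against.** The best defence is that the plan means a direct arm test for Aim 2c and did not write it out. The opening sentence of Data Analysis speaks of comparing the groups at months 9 and 18. Difference-in-differences ordinarily presupposes a baseline, so it fits only the aims that keep one. The GEE comparison names no interaction. The power calculation uses one time point, where only an arm term can be tested. This is good evidence of intent, and an analyst would probably act on it. But the opening sentence names visits, and the sentences after it define the comparison as the interaction. The GEE analysis is additional and its tested term is unstated. Nothing names a contrast for Aim 2c.

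Three stronger readings are tempting, and the documents do not support them.

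- A reader might infer that the planned test cannot detect any effect on pregnancy. That holds only if the odds ratio is the same at both visits. The documents do not give the timing of the effect, and the five sessions fall within 3 months of an 18-month follow-up.
- A reader might infer that the plan enters month-9 and month-18 records for Aim 2c. No section says so. Section 6 and item c of the sample size text describe one outcome over the whole period.
- A reader might infer that the effect cannot be estimated from the data in the model. It can: the month-18 arm contrast is available from the same records. What is missing is the named contrast.

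**Conclusion.** The concern stands in this form: the only comparison named for the binary outcomes is the time-by-arm interaction, Aim 2c is denied the baseline record that gives it meaning, and no other test is named for Aim 2c. With two records the interaction estimates change in effect between visits; with one record it is undefined. For the planned effect it rejects in about 5% of trials, against about 91% for the 18-month arm contrast behind the stated 89.5%.

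These figures assume two-sided alpha 0.05, 480 per arm, kappa 0 and constant hazard. They come from a marginal two-visit model rather than the full mixed model. If the effect grows or fades, the interaction rejected in 35% to 69% of trials in the scenarios tried, without tracking the overall benefit. This should be corrected before analysis, because a stated rule applied as written gives the wrong answer for one of the three hypotheses.

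**What to change.** Add to Section 9, Data Analysis, text along these lines:

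> *The time-by-arm interaction test applies to Aims 2a and 2b only. For Aim 2c the outcome is any unintended pregnancy over the 18-month follow-up, one record per woman, and the test is the arm effect in a logistic model with a random effect for cluster.*

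With one record per woman, the couple-level random effect drops out. This agrees with hypothesis (c) in Section 6 and with the comparison powered in item c. A month-18 arm contrast on cumulative status within the longitudinal model would also serve, provided one option is named in advance. State the tested term for Aim 2c in the GEE analysis, and the alpha for the primary tests. Limit the remark about higher power in the longitudinal analyses to the aims it applies to. The cost is a few sentences, with no new data, visits or participants.

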## **Quantitative Data Collection:**

Survey and urine pregnancy test data (from wives) will be collected from all enrolled couples in the CHARM2 RCT evaluation study. Both intervention and SOC arm participants will provide survey data at baseline and 9 & 18 month follow-ups. Survey data will be collected electronically on tablets using a unique identifier to link data between couples and across time. Wives in both the intervention and the SOC arms will be tested for pregnancy using a urine specimen at baseline and at both post-test timepoints; these data will directly be entered into the password protected electronic survey system at the time of survey data collection. Urine samples for pregnancy testing will not be retained for the study, but will be disposed of in disposal facilities upon completion of the test. Survey and pregnancy test results data will be stored locally on the tablet and, when internet is available, uploaded to the password-protected server. Separately, a list of contact names with unique identifiers will be maintained for tracking purposes; a hard copy form of this list will be kept in a locked file in [name] locked office at NIRRH. Baseline and follow-up surveys will be collected from couples using measures from the original CHARM study, which was based on India's Demographic and Health Survey (DHS/India's NFHS-3) and other validated measures. Couples must meet the eligibility criteria outlined below.

Eligible couples will be:

- Young wives (aged 18-29 years) and their husbands
- couples fluent in Marathi and both willing to participate
- no sterilization or infertility indicated (infertility is defined as having no pregnancy for 1+ years despite non-use of traditional or modern contraception)
- no pregnancy or female/male surgical sterilization planned for the next 18 months, and no reported use of consistent use of modern contraceptives in the past three months, and
- residing in the village for at least 2 years and residing together for at least 3 months, to facilitate follow-up tracking

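### Aim 2a: the 83.3% power is for an 18-month-only comparison, and the statement that the planned time-by-arm test has more power has no calculation and fails if baseline use is low

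*Combined protocol and SAP*

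**What the plan says.** Section 9, Data Analysis, sets a mixed-effects longitudinal logistic regression with random effects for couple and geographic cluster and a categorical time effect. It says "Baseline will be included as a time point (Aims 2a, 2b only", so baseline use is an outcome in the model rather than a covariate. The arms are compared by difference-in-differences: "Statistically, this amounts to testing for an interaction between time and treatment arm in the longitudinal model". It adds "No other covariates will be included in the primary analysis". A GEE logistic comparison is also planned. The text does not say whether the interaction tested is the 18-month contrast, an average of 9 and 18 months, or a joint 2-df test.

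Section 9, Sample size considerations, item a, expects 40% modern use in control at 18 months and states "This study will have 83.3% power to detect an absolute difference of 12% or more between treatment groups at follow-up". It then explains that "for power calculations we considered only the 18-month time point in a model similar to those to be used in the analyses" and concludes "Power for the prescribed longitudinal analyses will be higher".

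The eligibility list under Quantitative Data Collection requires "no reported use of consistent use of modern contraceptives in the past three months". No expected baseline rate of use, within-couple correlation or 9-month effect is given. Section 6 words the outcome as "Use contraception (including LARC) at 9 & 18-month follow-ups; effects on LARC will be explored", while the power item counts modern methods only.

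**The concern.** Power was worked out for one test and a different test is primary. The only link between them is an unconditional sentence that the second has more power.

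Repeated measures often add power, but not always here. A logit-scale difference-in-differences is the 18-month arm difference in log-odds minus the baseline arm difference. A log-odds estimated from few users has a large variance, and subtracting it adds that variance to the test. Within-couple correlation gives some back. Because consistent modern users are excluded, low baseline modern use is plausible, although inconsistent users can enrol and no rate is stated.

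If baseline use is low, a real 12-point effect could be reported as non-significant although the comparison that was powered would probably have detected it.

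**Working it through.** **Inputs from the plan.** 1200 couples enrolled and 960 observed after 80% retention. 40% vs 52% at 18 months. Total kappa 0.10. The interview samples (50 couples at 5 per intervention cluster, 20 at 2 per control cluster) imply 10 clusters per arm. That gives 600 couples per arm at baseline and 480 at follow-up. The sample-size sentence attaches its 20 clusters to each arm, but its own n=960 fits 20 clusters in total, and that is used here.

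**Assumptions, because the plan is silent.** Two-sided alpha 0.05; baseline use 2% to 20%; couple SD 0.3 to 3 on the logit scale; the same effect at 9 and 18 months; a cluster effect that is constant over time and so cancels (which favours the interaction).

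**Step 1, the plan's own figure.** Reading kappa as a between-cluster coefficient of variation, the variance per arm is [p(1-p)/48 + (0.10p)²]/10.
- Control: (0.0050 + 0.0016)/10 = 0.00066.
- Intervention: (0.0052 + 0.0027)/10 = 0.00079.
- SE = √0.00145 = 0.0381, and 0.12/0.0381 = 3.15.
- Noncentral t with 18 df gives 84.6%, close to 83.3%.

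Read as an intra-cluster correlation, kappa would give 34% (0.10) or 53% (0.05), so the definition should be stated. The point below does not depend on it.

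**Step 2, closed form for the 18-month interaction with no within-couple correlation.**
- Effect: logit(0.52) - logit(0.40) = 0.486.
- 18-month variance: 1/(480×0.40×0.60) + 1/(480×0.52×0.48) = 0.0170.
- Baseline variance: 2/(600·p·(1-p)).
- Power: Φ(0.486/√(sum of the two variances) - 1.96).

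| Baseline use | Baseline variance | Total | Power | Ceiling if 18-month use were known exactly |
|---|---|---|---|---|
| 2% | 0.1701 | 0.1871 | 20% | 22% |
| 5% | 0.0702 | 0.0872 | 38% | 45% |
| 10% | 0.0370 | 0.0541 | 55% | 71% |
| 20% | 0.0208 | 0.0379 | 70% | – |

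At 5% the baseline term rests on 600×0.05 = 30 users per arm. Letting the within-couple correlation run from 0 to 0.5, capped at what the two rates allow, gives 20-22%, 38-44%, 55-71% and 70-91%.

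**Step 3, the planned mixed model.** Expected information was computed for a logistic model with couple random intercept, arm, categorical time and arm-by-time, with the couple SD estimated, 480 complete and 120 baseline-only couples per arm. Intercepts were set so that the marginal rates are p at baseline and 40% vs 52% at both follow-ups. Ranges run over couple SD 0.3 to 3.

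| Contrast | 2% | 5% | 10% | 20% |
|---|---|---|---|---|
| 18 months | 21-39% | 39-62% | 56-80% | 71-93% |
| Average of 9 and 18 months | 22-40% | 42-66% | 64-85% | 82-97% |
| Joint 2-df | 17-31% | 33-56% | 53-77% | 73-93% |

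At couple SD 1 and 2 the 18-month contrast has 47% and 58% at 5% baseline use, and 78% and 88% at 20%. Fitting the mixed model to simulated trials (300 per setting, error about 3 points) gave 43% and 58% at 5%, and 75% and 88% at 20%. The 18-month-only model had 84% on the same data.

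**Step 4, what moves the answer.**
- Baseline use needed to reach 83.3%: averaged contrast, 9% (SD 3) to 22% (SD 0.3); joint test, 12% to 37%; 18-month contrast, 12% (SD 3), 15% (SD 2), 31% (SD 1), and not reached at SD 0.3, where the maximum is 80%.
- If half the cluster variance is specific to each time point, the 18-month contrast falls to 20-36%, 35-55%, 50-70% and 61-82%.
- An exception in the other direction: with no 9-month effect at all, the joint test has 67-94% at 2% baseline use, because the 9-to-18-month change then carries the information.

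**The case against.** The strongest reply is that baseline use may not be low. Only consistent modern users are excluded, so occasional pill or condom users can enrol. Control use is expected to reach 40% at 18 months under standard care, and starting from 2-5% would be an 8- to 20-fold rise. At 20% baseline use the averaged contrast has 82-97%. The lowest figures also use couple SD 0.3, a baseline-to-18-month correlation near 0.01, which makes a woman's use almost independent over time. All of this stands. A reader might infer that the trial is underpowered for Aim 2a, at 21-62%. The documents do not support that, because they give neither the baseline rate nor the correlation. The same gap leaves the plan's sentence without support.

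A reader might also infer that the interaction is the wrong primary test and must be replaced. That does not follow either. Section 11 has unblinded staff recruiting after clusters are randomised, and the interaction removes a time-constant baseline difference between arms. An 18-month contrast adjusted for the woman's baseline use does not. In simulation with no true effect but baseline use of 5% vs 6%, or 10% vs 12%, its false-positive rate was 14-19%. Assuming a common baseline mean for both arms is open to the same recruitment problem. Section 9 also sets the same model for Aim 2b, so changing Aim 2a alone would give the two outcomes different primary tests.

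Finally, none of these figures includes the imputation of missing follow-up from the worse half of each arm (Section 9, Quantitative Data Collection). Taken literally with 20% missing, control becomes 0.8×40% = 32%. Intervention becomes 0.8×52% + 0.2×4% = 42%, because only 2 points of its lower 50 are users. The effect being powered would therefore change too.

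**Conclusion.** The concern holds as a mismatch between the powered test and the primary test, joined by a sentence that is not true in general. The mismatch is plain from the text. Its size is conditional. Under the stated assumptions the interaction falls well short of 83.3% at 2-5% baseline use for every contrast when the effect is the same at 9 and 18 months. At 10% only the averaged contrast can reach 83.3%, and only with high within-couple correlation. From about 20% the sentence may be right. It is unsupported rather than always false. The interaction remains a valid and defensible test; what is missing is a power statement for it. This should be fixed. Confidence is moderate, because the baseline rate, within-couple correlation, 9-month effect and cluster-by-time variance are all unstated.

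**What to change.** In Section 9:

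1. Under Sample size considerations, delete the sentence that longitudinal power will be higher, and say plainly that 83.3% refers to an 18-month-only comparison.
2. In its place give simulated power for the interaction that will be tested, with the planned imputation applied. State the assumed baseline rate (or a range), within-couple correlation, 9-month effect and any cluster-by-time variance.
3. Under Data Analysis, name the contrast: 18 months, the average of 9 and 18 months, or joint 2-df.
4. State which methods count as use. If traditional methods count, baseline use is higher and the problem shrinks.
5. Prespecify, as a supporting analysis beside the interaction, the 18-month arm contrast adjusted for the woman's baseline use, and report baseline use by arm. Without the imputation and with no baseline difference between arms, its simulated power was 83-96% across 2-20% baseline use.

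Making that adjusted contrast primary is an option for the sponsor, not a required correction. It would mean amending the rule against other covariates, giving up protection against recruitment imbalance, and deciding what to do for Aim 2b.

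The cost is SAP wording and one simulation, with no new data or visits, and possibly a less favourable power figure.

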## 10. HUMAN SUBJECTS

**NOTE: All subjects will be enrolled at Non-UCSD sites.  
All participants will be of Indian heritage, and enrolled into the study in India.**

**Inclusion of Pregnant Women:** Pregnant women will be included in this study, as the methods meet criteria for their inclusion, including posing no increased risk for the pregnant women or the fetus, beyond that seen for non-pregnant women. Additionally, study findings can support the health of pregnant women, and the study is in no way designed to influence the woman with regard to her choices for the index pregnancy. No additional protections for pregnant women are included, as the existing protections for all wives address risks for pregnant wives (e.g., risk for partner violence).

**Inclusion of Children:** Adolescent wives or husbands included in this study meet the federal definition of children, as they may be under age 21 years. Due to heightened vulnerability in households, very young wives (<18 years) will not be included in this study. We include this population of children as part of our research, but do so without parental consent as they are married and recognized as adults able to provide consent on their own. Study findings specifically support the health and safety of this young population. Existing protections outlined for all wives consider the heightened vulnerabilities young wives face in marriage. Thus, no additional protections are provided beyond that described above. Nonetheless, we have not included wives < 18 years, as the assessments used in this study are not necessarily tailored to the unique needs, sensitivities or cognitive capacities of these younger wives. Further, they are a more vulnerable group that may require greater support than is provided in this study. Our original CHARM study did not identify any wives this young in recruitment.

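### The secondary adjusted analysis selects covariates at 0.15 from an open list that names pregnancy and recent childbirth without fixing them at baseline

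*Combined protocol and SAP*

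**What the plan says.** The Data Analysis paragraph of section 9 keeps the primary comparison to time and arm: "No other covariates will be included in the primary analysis". It then adds a further layer: "However, we will also conduct secondary analyses". These adjust for "potentially relevant covariates (e.g., age, current pregnancy, past year child- birth, etc", and the covariates enter "in addition to time and treatment arm, using backward model selection at the" 0.15 level. The stated aims are better precision and less bias from chance imbalance between arms.

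The model is longitudinal, with a categorical time effect. For Aims 2a and 2b, baseline is one of the time points and the treatment effect is the time-by-arm interaction.

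On when pregnancy is known, section 9 (Procedures/Activities for Participants) says: "Female participants (wives) will also take urine pregnancy tests at baseline, and 9 &18-month follow-up". The Quantitative Data Collection text says the same of both arms: wives are "tested for pregnancy using a urine specimen at baseline and at both post-test timepoints". Section 10 states: "Pregnant women will be included in this study". Baseline pregnancy will therefore vary between women and is a usable covariate. No part of the documents gives a closed covariate list or says which visit's value is meant.

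**The concern.** There are two separate weaknesses.

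**Timing.** In a repeated-measures model, current pregnancy can be read as the value at each visit. The follow-up value arises after randomisation, and hypothesis (c) in section 6 says CHARM2 changes it. Past-year childbirth has the same problem, because at the 18-month visit it covers births after enrolment. Conditioning on such a variable can absorb part of the effect on contraceptive use. For Aim 2c it conditions on part of the outcome. The selection rule gives no protection. A variable that strongly predicts non-use will tend to be kept, and if it predicts non-use perfectly the logistic fit can suffer separation.

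**Selection.** Backward elimination keeps covariates by their association with the outcome. It can therefore drop one that is imbalanced between arms, although correcting imbalance is one of the two stated aims. It can also leave different sets for different outcomes. Because the list is open, a reader cannot check that the reported set was not chosen after the fact.

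At stake is how far the adjusted results can be trusted as support for the primary ones.

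**Working it through.** **1. Calibrating the clustering.** The stated powers are not in dispute; they were reproduced to set the clustering for step 4. The inputs are the rates and kappas in section 9, Sample size considerations. Assumed: two-sided 0.05, 10 clusters of 48 per arm, kappa as a variance on the logit scale split equally between levels, and 4 to 8 villages per cluster. A normal approximation gives:

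- (a) contraception: 81.4–83.0%, stated 83.3%
- (b) MSV: 91.7–91.9%, stated 91.5%
- (c) unintended pregnancy: 91.1%, stated 89.5%

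**2. Contraception effect if visit-level pregnancy is adjusted for.** Inputs from the same section: use 40% vs 52%; no unintended pregnancy 90% vs 95.5%, so 10% vs 4.5% with one. Assumed: pregnant women are non-users, and a share f of these pregnancies is current at the visit in both arms. Pregnant women then carry no information on use, so the adjusted effect is the effect among non-pregnant women:

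use among non-pregnant = use / (1 − f × unintended pregnancy)

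| f | Control | CHARM2 | Difference (points) | Odds ratio | Log odds ratio lost |
|---|---|---|---|---|---|
| none | 40% | 52% | 12.0 | 1.625 | – |
| 0.25 | 0.40/0.975 = 41.03% | 0.52/0.98875 = 52.59% | 11.6 | 1.595 | 4% |
| 0.5 | 0.40/0.95 = 42.11% | 0.52/0.9775 = 53.20% | 11.1 | 1.563 | 8% |
| 1 | 0.40/0.90 = 44.44% | 0.52/0.955 = 54.45% | 10.0 | 1.494 | 17% |

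The loss comes from the difference in pregnancy between arms, not from conditioning as such. With 10% pregnant in both arms, use would be 0.40/0.90 = 44.44% vs 0.52/0.90 = 57.78%, an odds ratio of 1.711, which is above 1.625.

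**3. Aim 2c.** The unadjusted odds ratio is (0.045/0.955)/(0.10/0.90) = 0.424. If every current pregnancy is unintended, the odds among non-pregnant women are (1 − f)p/(1 − p) in each arm. The factor (1 − f) cancels and the ratio stays 0.424. A share f of the events then contributes nothing, and at f = 1 the effect cannot be estimated.

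**4. Does selection distort the test of arm?** The check used 4,000 simulated null trials per scenario: 20 clusters of 48, a 40% event rate, and cluster SD 0.20 or 0.32 on the logit scale. Those are variances of 0.04 and 0.10, which bracket the cluster half of kappa, 0.05. Arm was forced in, 5 to 10 candidates were offered of which 3 were prognostic, and a random-intercept linear approximation at 18 months was judged against a t distribution. Type I error for arm:

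- individual-level baseline candidates only: 3.9–5.2% with backward selection at 0.15, 3.7–5.3% with the full fixed set; the gap is under 0.2 points in every scenario
- 2 to 4 cluster-level candidates in the pool: 5.8–9.0% with selection, 5.5–7.7% with the fixed set; selection adds about 0.3–1.3 points

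The Monte Carlo standard error near 5% is √(0.05 × 0.95/4000) = 0.34 points. The number and strength of candidates are assumed.

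**The case against.** The other side is strong on several points.

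- **Status.** These analyses are labelled secondary, and the primary result contains no covariates. This stands.
- **Validity of the p-values.** A reader might infer that selection at 0.15 invalidates the test of the intervention. The documents do not support that. Covariates are added to time and arm, the three named examples are all individual-level, and step 4 shows an essentially unchanged type I error for such candidates when measured at baseline. Inflation appeared only with several cluster-level candidates, which the plan does not name, and the fixed set was also above nominal there.
- **The planned contrast.** For Aims 2a and 2b, main effects of baseline covariates hardly move the time-by-arm interaction. In a small simulation (150 runs per scenario, covariate strengths and baseline rates assumed, independence GEE), going from no covariates to three changed the 18-month interaction by 0.011 on the log-odds scale on average and by 0.036 at most, against a standard error of 0.16–0.20. Which baseline covariates survive therefore matters little for those aims. The check does not cover Aim 2c, which has no baseline time point.
- **The baseline reading.** A reader might also infer that the plan does adjust for follow-up pregnancy. It does not say so. Correcting chance imbalance suggests baseline values, and women can be pregnant at enrolment. On that reading nothing is adjusted away.
- **Size.** A 17% loss needs every unintended pregnancy of the 18 months to be ongoing at the last visit. With evenly spread conceptions and nine-month pregnancies, about 9/18, or half, would be.

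What remains is that the text permits both readings, one of them biased, and that the list is open.

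**Conclusion.** The point holds as a low-priority defect in a secondary analysis. The covariate list is open, selection depends on the data, and two named candidates have no time of measurement.

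If follow-up values were used, the adjusted contraception effect would shrink by about 4–8% on the log-odds scale when a quarter to a half of the unintended pregnancies are current at the visit, with 17% as the extreme. Aim 2c would be adjusted for part of its own outcome. If baseline values are meant, none of the treatment effect is removed. What is left is then that selection can drop an imbalanced covariate, which matters mainly for Aim 2c, and that sets may differ between outcomes.

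The sizes rest on the plan's design rates, on pregnant women counting as non-users, and on the assumed share f. The documents give no recall window for contraceptive use. If the measure looks back over a period, some pregnant women could count as users and step 2 would not apply exactly.

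**What to change.** In section 9, Data Analysis, replace backward selection with a short fixed set: wife's age, pregnancy status at baseline, and birth in the year before baseline. State that only baseline values are used and that the same set applies to all outcomes. Write it down before outcome data by arm are seen, which here means before the interim efficacy analysis described in section 15. Follow-up pregnancy should appear as an outcome and not as a covariate.

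Do not add the baseline value of the outcome as a covariate for Aims 2a and 2b. Baseline is already a time point in that model, so the baseline row would be predicted by itself.

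The cost is about one sentence. A weak covariate may stay in the model, at negligible cost with about 960 observed couples. Sample size, data collection and the primary analysis do not change.
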